The most common treatment-emergent adverse events (TEAEs) were gastrointestinal (GI) events, including vomiting (with higher doses), abdominal distention, and nausea, which were dose dependent, mostly mild in severity, occurred within 4 days of dosing, and resolved within a week of onset. Dose-dependent increases in heart rate (HR) and decreases in systolic blood pressure (BP) were observed, which returned to near baseline by Day 29.

Across dose levels, the maximum observed drug concentration (C_{max}) occurred between ~1 and 3 days postdose, while the mean terminal half-life was ~5 to 7 days, thus supporting a QW dosing regimen.

Study J1I-MC-GZBB (GZBB) is a Phase 1, randomized, investigator- and participant-blind study that assessed the safety, tolerability, and PK/PD effects of multiple doses of LY3437943 when administered QW in participants with T2D. Trulicity[®] (dulaglutide) 1.5 mg was used as an active comparator. Participants in Cohorts 1 to 3 received fixed doses of LY3437943 (0.5, 1.5, and 3 mg QW) or placebo for 12 weeks. Participants in Cohorts 4 and 5 received placebo or LY3437943 titrated from a starting dose of 3 mg QW to maximum doses of 6 mg QW (Cohort 4) and 12 mg QW (Cohort 5) over the 12-week treatment period.

Based on preliminary data from this ongoing study, 72 participants received study treatment, and 43 completed the study to date. Gastrointestinal adverse events (AEs) (nausea, abdominal distention, and diarrhea) and decreased appetite were the most frequently reported events, mostly mild in severity and dose dependent. A dose dependent increase in HR was noted. The HR effects were consistent with those of the GLP-1 or GIP/GLP-1RA class, as was seen in Phase 1 clinical development. There were no reports of severe hypoglycemia or AEs related to the site of injection. Overall, data from early phase clinical trials support further development of LY3437943 in Phase 2 studies.

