8.3.1. Timing and Mechanism for Collecting Events

The following table describes the timing, deadlines, and mechanism for collecting events.

Event	Collection Start	Collection Stop	Timing for Reporting to Sponsor or Designee	Mechanism for Reporting	Back-Up Method of Reporting
Adverse Event					
AE	Signing of the ICF	Participation in study has ended	As soon as possible upon site awareness	AE eCRF	N/A

Event	Collection Start	Collection Stop	Timing for Reporting to Sponsor or Designee	Mechanism for Reporting	Back-Up Method of Reporting
Serious Adverse Event					
SAE and SAE updates – prior to start of study intervention and deemed reasonably possibly related with study procedures	Signing of the ICF	Start of intervention	Within 24 hours of awareness	SAE eCRF	SAE paper form
SAE* and SAE updates – after start of study intervention	Start of intervention	Participation in study has ended	Within 24 hours of awareness	SAE eCRF	SAE paper form
SAE* – after participant’s study participation has ended and the investigator becomes aware	After participant’s study participation has ended	N/A	Promptly	SAE paper form	N/A

Event	Collection Start	Collection Stop	Timing for Reporting to Sponsor or Designee	Mechanism for Reporting	Back-Up Method of Reporting
Pregnancy					
Pregnancy in female participants and female partners of male participants	After the start of study intervention	2 months after last injection for female participants and 4 months after last injection for female partners of male participants	Within 24 hours of learning of the pregnancy	SAE eCRF	SAE paper form
Product Complaints					
PC associated with an SAE or might have led to an SAE	Start of study intervention	End of study intervention	Within 24 hours of awareness	Product complaint form	N/A
PC not associated with an SAE	Start of study intervention	End of study intervention	Within 1 business day of awareness	Product complaint form	N/A
Updated PC information	—	—	As soon as possible upon site awareness	Originally completed product complaint form with all changes signed and dated by the investigator	N/A

Event	Collection Start	Collection Stop	Timing for Reporting to Sponsor or Designee	Mechanism for Reporting	Back-Up Method of Reporting
PC (after participant's study participation has ended and the investigator becomes aware)	After participant's study participation has ended	N/A	Promptly	Product complaint form	N/A

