8.3.2.5. Deaths

All deaths will be adjudicated by a committee of physicians external to Lilly. This committee will be blinded to treatment assignment.

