8.9. Immunogenicity Assessments

At the visits and times specified in the SoA (Section 1.3), venous blood samples will be collected to determine antibody production against LY3437943. Antibodies may be further characterized for cross-reactive binding to endogenous counterparts (native GIP, GLP-1, and glucagon), and their ability to neutralize the activity of LY3437943 and endogenous counterparts. To interpret the results of immunogenicity, a venous blood sample will be collected at the same time points to determine the concentrations of LY3437943. All samples for immunogenicity should be taken predose when applicable and possible.

Treatment-emergent ADAs are defined in Section 9.4.4.4. If the immunogenicity sample at the last scheduled assessment or discontinuation visit is TE-ADA positive, additional samples may be taken until the ADA signal returns to baseline (that is, no longer indicates TE-ADA) or up to 1 year after last dose. A PK sample may be collected at each time point at the investigator's discretion.

Samples will be retained for a maximum of 15 years after the last participant visit, or for a shorter period if local regulations and ERBs allow, at a facility selected by the sponsor. The duration allows the sponsor to respond to future regulatory requests related to the LY3437943. Any samples remaining after 15 years will be destroyed.

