10.1.8 Study and Site Start and Closure

10.1.8.1 Discontinuation of the Study

The sponsor designee reserves the right to terminate the study at any time for any reason at the sole discretion of the sponsor. The study will be discontinued if Lilly or its designee judges it necessary for medical, safety, regulatory, or other reasons consistent with applicable laws, regulations, and GCP.

Medical Oversight and Safety Review

Ongoing safety review(s) by designated sponsor personnel will occur and be documented. Such reviews will include

- monitoring and assessing the safety information collected during the trial both in real time and periodically
- reviewing safety data for trends that need action, and
- detecting adverse drug/device effects.

A safety investigation will be triggered to determine if the study should be terminated early based on the following criteria

- two study participants develop the same TEAE or SAE considered possibly or probably related to study drug that is severe or medically significant but not immediately life-threatening; or where hospitalization or prolongation of hospitalization is indicated; or is disabling; or limits self-care activities of daily living
- one study participant develops any TEAE or SAE regardless of attribution to study drug that has life-threatening consequences or requires urgent intervention
- death of any study participant at any time, and
- any other clinically significant safety signal.

If the study is prematurely terminated or suspended, the sponsor shall promptly inform the investigators, the IECs/IRBs, the regulatory authorities, and any contract research organization(s) used in the study of the reason for termination or suspension, as specified by the applicable regulatory requirements. The investigator shall promptly inform the participant and assures appropriate participant therapy and/or follow-up.

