For continuous measures, summary statistics will include sample size, mean, SD, median, minimum, and maximum for both the actual and the change from baseline measurements. LS means and standard errors derived from the analysis models will also be displayed for the change from baseline measurements. Treatment comparisons will be displayed showing the treatment difference LS means and the 95% CIs for the treatment differences, along with the p-values for the treatment comparisons. All baseline measures will be analyzed using an analysis of variance model that has treatment group as the model terms.

For categorical measures, summary statistics will include sample size, frequency, and percentages. A logistic regression model will be used to examine the treatment difference in binary efficacy outcomes with missing endpoints imputed. Fisher's exact test or Pearson's chi-square test will be used for treatment comparisons in other categorical outcomes.

For laboratory values, both CN and SI units will be presented. For body weight, kilogram (kg) will be presented.

Summary statistics for discrete count measures will include sample size, mean, SD, median, minimum, and maximum.

Kaplan-Meier method will be used for estimation of cumulative event-free survival rates over time, and Cox proportional hazards regression analysis will be used to compare hazards rates among treatments. In Kaplan-Meier estimation, the dose-pooling strategy will be used: subjects in the pre-specified analysis set with the same pre-planned titration history will be pooled together to calculate the number of events and the total number of subjects at risk.

Unless otherwise specified, baseline is defined as the last nonmissing measurement prior to first dosing of the study drug, or prior to the randomization date for the subjects who are randomized but never dosed.

End of study participation for a participant will be the earliest of date of death, date of withdrawal from further participation in the study, or date of safety follow-up visit (Visit 801). For participants considered to be lost-to-follow-up, end of study participation will be the date of lost-to-follow-up reported by the investigator. Participant data included in the database after the last date of study participation (including safety follow-up period) will be excluded from statistical analysis.

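### The SAP's end-of-participation cut-off has no safety exception, so deaths and SAEs that start during washout in participants who leave without Visit 801 drop out of the by-arm safety counts

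*SAP*

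**What the plan says.** SAP 4.1 defines the cut-off: "End of study participation for a participant will be the earliest of date of death, date of withdrawal from further participation in the study", or the date of Visit 801. For participants lost to follow-up, "end of study participation will be the date of lost-to-follow-up reported by the investigator". It then applies one rule to everything later: "Participant data included in the database after the last date of study participation (including safety follow-up period) will be excluded from statistical analysis". Neither the safety analysis set in SAP Section 3 nor the safety methods in SAP 4.6 restores any later data. The safety set covers the treatment period plus safety follow-up, with no fixed number of days after the last dose.

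The protocol expects safety information to arrive after that date:

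- Section 8.3.1 has a reporting row for SAEs where "study participation has ended and the investigator becomes aware", on a paper form.
- Section 8.3.2.5 says: "All deaths will be adjudicated by a committee of physicians external to Lilly".
- Section 10.1.8.1 lists "death of any study participant at any time" among the triggers for a safety investigation.
- Section 8.9 says that, in participants still positive for treatment-emergent antibodies at the last scheduled or discontinuation sample, "additional samples may be taken until the ADA signal returns to baseline (that is, no longer indicates TE-ADA) or up to 1 year" after the last dose.

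On exposure, Protocol 2.2 reports that "the mean terminal half-life was ~5 to 7 days".

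**The concern.** Protocol 7.2 ends study drug and study participation together when a participant withdraws. The safety window therefore closes on the withdrawal date, with no lag for drug still on board. If that person dies two weeks later, withdrawal is the earlier date. The death is then outside the analysis, even if it has been reported and adjudicated.

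SAP 1.1 sets the safety question over treatment plus follow-up, irrespective of adherence. Under the cut-off, participants who leave outright are counted for a shorter post-dose period than completers. The by-arm death and SAE counts could therefore disagree with what the sponsor's safety records and the adjudication committee hold. With about 60 participants per dose, one death or SAE matters to how an arm is read.

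**Working it through.** **Inputs**

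- Half-life of about 5 to 7 days (Protocol 2.2).
- Five half-lives stated as 30 days (Protocol 10.5).
- Safety follow-up sample at 5 weeks after the last dose (Protocol 1.3, pharmacokinetic schedule).
- About 300 randomized 2:1:1:1:1:2:2, with 20% dropout (Protocol 9.2; SAP Section 5).
- Assumptions, not in the documents: the share leaving without Visit 801, and an SAE rate of 5 to 10 per 100 person-years.

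**Reproducing the plan's figures**

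- Five half-lives: 5 x 5 = 25 days, 5 x 6 = 30 days, 5 x 7 = 35 days. The stated 30 days is the midpoint.
- Completers per dose: 300 x 2/10 = 60, and 60 x 0.8 = 48, as stated.

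**Drug remaining after the last dose**, 0.5^(days / half-life), for half-lives of 5 and 7 days:

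| Days since last dose | Fraction remaining |
|---|---|
| 7 | 38% to 50% |
| 14 | 14% to 25% |
| 28 | 2% to 6% |
| 35 | 1% to 3% |

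**Who is covered**

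- Completers: last dose at Week 47, Visit 801 at Week 52, so (52 - 47) x 7 = 35 days, or 5 to 7 half-lives.
- Early stoppers who attend Visit 801, planned 4 weeks after their last treatment-period visit (Protocol 4.1.1): nominally at least 28 days, or 4 to 5.6 half-lives.
- Outright withdrawers with no Visit 801: nothing after the withdrawal date.

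**Ceiling on the time lost in the active arms**

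- All dropouts: 300 x 0.20 = 60. Placebo is 2/10 of the randomization, so 60 x 2/10 = 12 are on placebo and 48 on active drug. (This 48 is unrelated to the 48 completers per dose.)
- If all 48 leave on the day of the last dose with no Visit 801: 48 x 35 = 1,680 days, and 1,680 / 365.25 = 4.6 person-years. At 25 days it is 1,200 / 365.25 = 3.3.
- If half attend Visit 801, the 35-day figure halves to 2.3 person-years.

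**Expected SAEs outside the counts**

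- 4.6 x 0.05 = 0.23 and 4.6 x 0.10 = 0.46.
- If half attend Visit 801: 2.3 x 0.05 = 0.12 and 2.3 x 0.10 = 0.23.

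**The case against.** The strongest reply is that these events are not hidden. The rule concerns statistical analysis. SAP 4.6.3 promises narratives for every randomized participant with a death or SAE and states no date limit. The MACE listing in SAP 4.6.7.10 includes time from last dose to the event. Late SAEs still reach the sponsor under Protocol 8.3.1. This stands: a reader might infer that such events appear in no safety output, and the documents do not support that. What remains is their absence from the tabulated counts, and the SAP's silence on whether the exclusion reaches narratives and listings.

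The affected group is also narrow. Participants who stop drug are kept in the study, and those who decline further visits are still asked to attend Visit 801. For loss to follow-up, nothing shows that the reported date falls close to the last dose. This stands too, and it limits the point to participants who leave without Visit 801.

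A reader might infer that higher-dose arms lose more of their at-risk time. Gastrointestinal events were dose dependent in Phase 1 (Protocol 2.2), so this is plausible. But the documents give no dropout by arm, and an event that leads someone to stop drug precedes the cut-off and is counted.

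A reader might also infer that the antibody results are compromised. They are not. The extra samples are optional and taken only in participants already positive, so the incidence table in SAP 4.6.7.5 is unchanged. Only duration and return to baseline are affected. For a completer, sampling can run to Week 47 + 52 = 99, which is 47 weeks past Visit 801, so some samples may postdate the final lock in any case.

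Finally, SAP 4.1 permits additional analyses. That is discretion rather than prespecification. With three unblinded interim reviews planned in SAP 4.8, whether to count a late death is better settled in advance.

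**Conclusion.** The point holds for participants who withdraw outright or are lost without Visit 801. Known deaths and SAEs with onset during their washout are left out of the death, SAE and special-interest counts by a stated rule that has no safety exception.

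The size is small: at most about 4.6 active-arm person-years and about 0.2 to 0.5 expected SAEs. That ceiling assumes every planned dropout leaves on the last-dose day, none attends Visit 801, washout lasts 35 days and SAEs occur at 5 to 10 per 100 person-years. Applying 35 days to all 60 dropouts would give 60 x 35 / 365.25 = 5.7 person-years, but that includes placebo participants, who have no drug exposure.

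Efficacy results are untouched. The change is worth making because the events at issue are deaths and SAEs and the remedy is cheap.

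**What to change.** Amend SAP 4.1 and the safety sections as follows:

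1. Exempt deaths, SAEs and adjudicated events from the end-of-participation exclusion.
2. Keep the main TEAE tables on the actively followed period, so that passively reported events are not mixed into the tested comparisons.
3. Add a separate by-arm summary or listing of all deaths and SAEs with onset after the end of participation. Show days since last dose and flag events within the 5-week post-dose span over which completers are followed. Leave out information covered by a withdrawn consent to future disclosure (Protocol 7.2). The 5-week flag is a reporting window, not a clinical rule.
4. State that narratives and listings are not subject to the exclusion.
5. Optionally, say where antibody follow-up results after Visit 801 will be reported.

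The cost is a few sentences of SAP text and one additional output. Late capture is passive and comes on paper forms, so those reports must be brought into the output, with a footnote saying that ascertainment after participation is incomplete.

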4.2. Participant Dispositions

A listing and summary of study disposition for all randomized participants will be provided at the primary database lock and final database lock, respectively. Frequency counts and percentages of all participants screened, randomized, and receiving at least 1 dose of study drug will be presented by treatment groups and dose escalation subgroups. A listing and summary of randomized participants not receiving study drug will be provided. All participants who discontinue the study and/or study drug will be identified, and the extent of their participation in the study will be reported. If known, a reason for their discontinuation will be given. The primary reasons for discontinuation will be listed and summarized by treatment groups and dose escalation subgroups. Kaplan-Meier plots of time to premature study discontinuation, premature study treatment discontinuation, and premature study treatment discontinuation due to AE will be provided based on all randomized population. Time-to-event analyses of premature study treatment discontinuation, study drug discontinuation due to AE, and study discontinuation may be conducted.

Details about the demographic and baseline characteristics, historical illnesses, and preexisting conditions, concomitant medications, treatment compliance, and important protocol deviations can be found in Appendix 1 (Section 7.1) through Appendix 5 (Section 7.5), respectively.

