4.3.3. Analyses for Supplemental Estimand(s)

The analysis related to a supplemental estimand, “hybrid estimand” (Section 1.1), will be conducted using data in the randomized population.

Hybrid estimand is defined as the treatment difference in the mean percent change in body weight from baseline at Week 24 between LY3437943 and placebo for the study target population with ICEs handled differently according to the reasons of the events as follows:

- Category 1: The ICEs of permanent discontinuation of study drug due to reasons unlikely related to the efficacy/safety outcomes will be handled by the hypothetical strategy.
- Category 2: The ICEs of permanent discontinuation of study drug due to lack of efficacy before study treatment discontinuation will be handled by the hypothetical strategy.
- Category 3: All other ICEs will be handled by the treatment policy strategy.

In this study, following ICH E9 (R1) guidance, a plan was made to collect informative treatment disposition reasons, through eCRF, for why data intended for collection are missing and classify them into categories 1 through 3 as shown in [Table GZBF.4.1](#) (ICH 2019).

Table GZBF.4.1. Treatment Disposition Reasons

Disposition Reason	Associated Sub-Categories	Category
Adverse event		3
Protocol deviation	Due to epidemic/pandemic	1
	Other	3
Pregnancy		3
Lack of efficacy		2
Other		3
Withdrawal by subject	Concern about study procedures/perceived risks	3
	Scheduling conflicts	1
	Subject is moving or has moved	1
	Personal issue unrelated to trial	1
	Due to epidemic/pandemic	1
	Other (option to include a specify field)	3
Physician decision	Concern about study procedures/perceived risks	3
	Scheduling conflicts	1
	Subject is moving or has moved	1
	Due to epidemic/pandemic	1
	Other (option to include a specify field)	3
Study terminated by sponsor		1
Site terminated by sponsor		1
Study terminated by IRB/ERB		1

Abbreviations: ERB = ethical review board; IRB = institutional review board.

To estimate the “hybrid estimand,” multiple imputation will be used to impute the corresponding missing potential outcome according to the missingness patterns (Table GZBF.4.2) with ICEs handled differently according to the reasons of the events.

When participants have missing values without ICEs, the missing values will be imputed using data from participants who do not have ICE or missing values.

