7.4. Appendix 4: Treatment Compliance

Listing and summary of prematurely discontinuing study treatment (including discontinuation reason) and discontinuing study will be provided by treatment groups and dose escalation subgroups. Kaplan-Meier plots of time to premature study treatment discontinuation and time to

premature study treatment discontinuation due to AE will be provided at Weeks 24 and 48 based on all randomized population. Kaplan-Meier plots of time to premature study discontinuation will be provided at Weeks 24 and 48 based on all randomized population. Time-to-event analyses of premature study treatment discontinuation, study treatment discontinuation due to AE, and study discontinuation may be conducted at Weeks 24 and 48.

If data warrants, the counts and percentages of participants who follow the planned dose escalation scheme, have dose interruption, or have dose de-escalation will be summarized for each treatment group and dose escalation subgroups. Listing of overdose of LY3437943 and placebo will be provided.

Per protocol, treatment compliance will be assessed every 4 weeks, or every 12 weeks after Visit 11, at the time of visits to the study site. Treatment compliance will be defined as taking at least 75% of the scheduled LY3437943 or placebo doses. Compliance at each treatment compliance assessment visit mentioned above and over the corresponding study period will be calculated using the number of doses administered (regardless of the actual dose in unit or mL administered) divided by the total number of doses expected to be administered $\times 100$ at the specific visit or over the corresponding study period, respectively. Treatment compliance will be summarized descriptively at each treatment compliance assessment visit and over the corresponding study period by treatment groups and dose escalation subgroups using the full analysis set.

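### The Kaplan-Meier plot of drug discontinuation due to AE has no stated rule for stops for other reasons; under usual censoring it slightly overstates the probability of stopping for an AE

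*SAP*

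**What the plan says.** SAP 4.2 lists three Kaplan-Meier plots: study discontinuation, treatment discontinuation for any reason, and "premature study treatment discontinuation due to AE will be provided based on all randomized population". SAP 7.4 (Appendix 4) repeats the AE-specific plot and adds times: "premature study treatment discontinuation due to AE will be provided at Weeks 24 and 48 based on all randomized population".

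The general method is in SAP 4.1: "Kaplan-Meier method will be used for estimation of cumulative event-free survival rates over time". For comparisons, "Cox proportional hazards regression analysis will be used to compare hazards rates among treatments". The same section adds a pooling rule for the curves: "subjects in the pre-specified analysis set with the same pre-planned titration history will be pooled together". Formal analysis of the AE endpoint is optional: time-to-event analyses of "study drug discontinuation due to AE, and study discontinuation may be conducted".

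Other ways to stop drug permanently are on record. Table GZBF.4.1 in SAP 4.3.3 includes lack of efficacy, "Withdrawal by subject", physician decision, protocol deviation and pregnancy. No section says whether these are censored in the AE curve, and no section mentions cumulative incidence or competing risks.

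Crude figures are also planned. SAP 4.2 states: "The primary reasons for discontinuation will be listed and summarized by treatment groups and dose escalation subgroups". The AE overview in SAP 4.6.2 gives numbers and percentages stopping treatment because of an AE. Protocol 9.4.2.1 asks for Kaplan-Meier only for study discontinuation and all-cause drug discontinuation; the AE-specific curve appears only in the SAP.

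**The concern.** Kaplan-Meier treats a censored participant as still able to have the event later. That is reasonable for someone still on drug at a data cut. It is not so for someone who has left the drug for good because of withdrawal or lack of efficacy. With those stops censored, one minus the curve answers a hypothetical question: how many would stop for an AE if nobody could stop for any other reason? It exceeds the probability that participants actually face whenever some other stops precede AE stops.

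Protocol 4.2 and 4.3 give tolerability of the escalation schemes as a purpose of the design, and a reader will naturally read AE-stop risks off the plot at Weeks 24 and 48. Those values would be higher than the tabulated percentages for the same event, with nothing in the SAP to explain why. The all-cause drug-discontinuation curve does not have this problem, because every permanent stop counts as the event.

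**Working it through.** **Inputs from the documents.** About 300 randomized. Allocation is 2:1:1:1:1:2:2 (Protocol 9.2; SAP 1.2 and 5 print six terms for seven arms, so the protocol ratio is used). Dropout is 20%, a single figure for all groups, with no split by reason. Treatment lasts 48 weeks.

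**The plan's own figure.** The ratio sums to 10, so each dose group (4 mg and 8 mg pooled) and placebo has 300 × 2/10 = 60. Then 60 × 0.8 = 48 completers, as stated. The documents state no AE-stop probability to reproduce.

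**Formulas.** Let D be the total probability of stopping drug by Week 48 and r the AE share of the stopping hazard, with both hazards constant. The total cumulative hazard is −ln(1−D).
- Actual probability of an AE stop (cumulative incidence): D × r.
- One minus Kaplan-Meier with other stops censored: 1 − (1−D)^r.
- Worst ordering, all other stops (o) before any AE stop (a): a / (1−o).

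**At D = 20%.** With r = 0.5 the cumulative incidence is 10.0%, and 1 − 0.8^0.5 = 10.56%, an overstatement of 0.56 points. With r = 0.1, 2.0% becomes 2.21%. With r = 0.9, 18.0% becomes 18.19%. Worst ordering with 10% and 10%: 0.10/0.90 = 11.1%, or 1.1 points.

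**Largest overstatement over all splits, in percentage points.** Totals of 30% and 40% are assumptions.

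| Total stops | Constant hazards | Participants in 60 | Worst ordering |
|---|---|---|---|
| 20% | 0.56 | 0.33 | 1.1 |
| 30% | 1.3 | 0.80 | 2.7 |
| 40% | 2.5 | 1.5 | 5.1 |

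**Earlier times.** At Week 24 the 10%/10% case has total 1 − 0.8^0.5 = 10.56%. The cumulative incidence is 5.28% and one minus Kaplan-Meier is 1 − 0.8^0.25 = 5.43%, a difference of 0.15 points.

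**Drug-placebo gap by Week 48.** Constant hazards; all splits are assumed and shown as AE%/other%.

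| Active | Placebo | Overstatement, active / placebo | Actual gap | Kaplan-Meier gap |
|---|---|---|---|---|
| 10/10 | 2/18 | 0.56 / 0.21 | 8.0 | 8.35 |
| 15/15 | 2/18 | 1.33 / 0.21 | 13.0 | 14.1 |
| 20/20 | 5/35 | 2.54 / 1.19 | 15.0 | 16.35 |
| 15/5 | 5/15 | 0.41 / 0.43 | 10.0 | 9.98 |
| 18/2 | 8/12 | 0.20 / 0.54 | 10.0 | 9.66 |
| 10/2 | 5/25 | 0.11 / 0.77 | 5.0 | 4.33 |

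The gap grows in the first three rows, is practically unchanged in the fourth, and shrinks in the last two.

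**Scale.** The standard error of one arm's crude proportion at n = 60, √(p(1−p)/60), is 3.9 points at 10%, 4.6 at 15% and 5.2 at 20%.

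**The case against.** The case for leaving the plan alone is a fair one. At the planned dropout the overstatement is about a third of one participant in 60, well inside sampling error. Escalation ends by Week 12, so AE stops may come early, which makes it smaller: with 10% AE stops confined to Weeks 0 to 12 and 10% other stops spread over 48 weeks (assumed), it is 0.14 points. The actual percentages are tabulated anyway. The curve is a disposition plot, and the formal comparison is optional. The SAP describes event-free curves and does not say that their complement will be reported as a risk. A Cox model that censors other stops is a valid analysis of the cause-specific hazard.

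All of this stands as to size and consequence. It does not remove the point: the AE-specific curve would still carry an avoidable upward error and disagree with the tables without explanation.

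A reader might go further and infer that the drug-placebo gap is exaggerated. The documents do not support that: they give no stop rates by arm or reason, and plausible splits move the gap either way. Nor do they show that the overstatement must differ between arms; 15/5 against 5/15 gives almost equal amounts. Finally, no section says that this plot decides the Phase 3 dose.

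**Conclusion.** The point holds as a small, inexpensive improvement. The SAP plans Kaplan-Meier for a single-cause stop, names no competing-risk method and leaves the handling of other stops unstated. Under the usual reading, one minus the curve overstates the probability of an AE-related stop by at most about 0.6 points by Week 48 at 20% total stops (about 1.1 under the worst ordering). At assumed totals of 30% to 40% the maximum is about 1.3 to 2.5 points (2.7 to 5.1 under the worst ordering). The direction of any effect on the drug-placebo gap cannot be determined from the documents.

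Three assumptions carry this. First, other stops are censored; that is convention, not a written rule. Second, hazards are constant except where the worst ordering is shown. Third, the 20% dropout also describes stops of study drug. Protocol 7.1 keeps participants in the study after they stop drug, so drug stops could exceed dropout, which is why the 30% and 40% rows are given.

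**What to change.** In SAP 4.2 and 7.4, replace the Kaplan-Meier plot for AE-related treatment discontinuation with the Aalen-Johansen cumulative incidence, treating permanent discontinuation for any other reason as a competing event. Censor only participants still on drug at the data cut or at completion. State that the pooling by planned titration history in SAP 4.1 applies to this estimator too. Without pooling, and with stop status known for everyone, the estimate equals the crude percentage; with pooling, a footnote should say that the curve for one arm need not equal its tabulated percentage.

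Keep Kaplan-Meier for all-cause treatment and study discontinuation. If the optional Cox comparison of AE stops is run, label it a cause-specific hazard ratio. If the Kaplan-Meier plot is retained, at least write down the censoring rule and say that its complement is not the AE-stop probability.

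The cost is a few lines of SAP text and minor programming, mainly to carry the pooling into the new estimator. Reasons for stopping are already collected, so no new data are needed.
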